### 7.3.5 Exploratory Analysis

The exploratory endpoints of interest are the Patient Eye Drop Experience Survey score at Day 14 and the change of OSDI score from baseline at Day 14. The score of each item in the Patient Eye Drop Experience Survey at Day 14 and the change of OSDI score from baseline at Day 14 will be summarized using descriptive statistics: mean, median, standard deviation, standard error of the mean (SEM), interquartiles, min and max. In the meanwhile, one bar plot for the mean of the score with 95% confidence interval will be made for each of the exploratory endpoints. The change of OSDI from baseline at Day 14 will be summarized using the same descriptive statistics. A descriptive p-value (paired t-test) will be calculated for the change of VAS score if the data is adequate.

Version date: 02 February 2023

#### 8.0 **Study Conduct**

#### 8.1 **Responsibilities Within the Study**

The study will be conducted by the Investigator and Lumanity under AbbVie oversight. The study shall be conducted as described in the approved protocol.

#### 8.2 **Protection of Human Subjects**

The study will be conducted in accordance with ethical principles that have their origin in the current Declaration of Helsinki and will follow the principles of International Conference Harmonization Good Clinical Practice (ICH GCP) and Good Epidemiology Practice (GEP) and applicable regulatory requirements. IRB/EC notification or approval will be obtained prior to the initiation of the study as necessary per local Regulation.

#### 8.3 Patient Information/Informed Consent

This study will be run in compliance with local laws and regulations. Notification/submission to the responsible Ethics Committee, and/or Competent Authorities will be performed as required by local laws and regulations (see Country Information page [Appendix A]).

Written informed consent will be obtained prior to patient inclusion.

#### **Safety Reporting** 9.0

Please notify AbbVie of any adverse event whether serious or nonserious and record the information in the provided AE/SAE Data Collection Form (Appendix F).

The AbbVie contact details are specified in Country Information page (Appendix A).

The following adverse event and safety information definitions and further information is provided should you need to report any safety information to AbbVie.

Version date: 02 February 2023

#### 9.1 Adverse Event Definition

An AE is defined as any untoward medical occurrence in a patient or clinical investigation patient administered a pharmaceutical product and which does not necessarily have a causal relationship with this treatment. An AE can therefore be any unfavorable and unintended sign (including an abnormal laboratory finding), symptom, or disease temporally associated with the use of a medicinal product, whether or not the event is considered causally related to the use of the product.

Such an event can result from use of the drug as stipulated in the protocol or labeling, as well as from "special situations" as accidental or intentional overdose, medication error, occupational or accidental exposure, off-label use, drug abuse, drug misuse, or drug withdrawal, all which must be reported whether associated with an adverse event or not. Any worsening of a pre-existing condition or illness is considered an AE and should be reported as a new AE.

#### 9.2 Serious Adverse Event Definition

If an adverse event meets any of the following criteria, it is considered a serious adverse event (SAE):

Death of Patient	An event that results in the death of a patient.	
Life-Threatening	An event that, in the opinion of the treating physician, would have resulted in immediate fatality if medical intervention had not been taken. This does not include an event that would have been fatal if it had occurred in a more severe form.	
Hospitalization or Prolongation of Hospitalization	An event that results in an admission to the hospital for any length of time or prolongs the patient's hospital stay. This does not include an emergency room visit or admission to an outpatient facility.	
Congenital Anomaly	An anomaly detected at or after birth or any anomaly that result in fetal loss.	

Version date: 02 February 2023

Persistent or Significant Disability/Incapacity An event that results in a condition that substantially interferes with the activities of daily living of a patient. Disability is not intended to include experiences of relatively minor medical significance such as headache, nausea, vomiting, diarrhea, influenza, and accidental trauma (e.g., sprained ankle).

Important Medical Event Requiring Medical or Surgical Intervention to Prevent Serious Outcome An important medical event that may not be immediately life-threatening or result in death or hospitalization, but based on medical judgment may jeopardize the patient and may require medical or surgical intervention to prevent any of the outcomes listed above (i.e., death of patient, life threatening, hospitalization, prolongation of hospitalization, congenital anomaly, or persistent or significant disability/incapacity). Additionally, any elective or spontaneous abortion or stillbirth is considered an important medical event. Examples of such events include allergic bronchospasm requiring intensive treatment in an emergency room or at home, blood dyscrasias or convulsions that do not result in inpatient hospitalization, or the development of drug dependency or drug abuse.

# 9.3 Serious and Nonserious Adverse Event Reporting

- For **serious adverse events** from patients using an AbbVie product notify AbbVie within 24 hours of the physician becoming aware of the event.
- For **nonserious adverse events** from patients using an AbbVie product notify AbbVie within 15 calendar days of the physician becoming aware of the event, including "special situations."

AbbVie contact details are specified in the Country Information page (Appendix A).

# 9.4 Patient Reported Outcomes and/or Quality of Life Questionnaires

Patient Reported Outcome (PRO) or Quality of Life (QoL) questionnaires data are not considered a potential source of adverse events for the purposes of this study. However,

Version date: 02 February 2023

the physician should review the PRO or questionnaire(s) data. If the physician identifies an adverse event and it is determined to be related to an AbbVie authorized product, report to AbbVie as described above and to the relevant Regulatory Authority, as required by local laws and regulations.

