# 6.4.2 Storage and Disposition of Study Drug

ABBV-444 must be stored as described in table above. The investigational products are for investigational use only and are to be used only within the context of this study. The study drugs supplied for this study must be maintained under adequate security and stored under the conditions specified on the respective drugs' label until dispensed for subject use or destroyed on site as appropriate.

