#### 11.2 **Complaint Reporting**

Product complaints concerning an AbbVie authorized product must be reported to AbbVie within 24 hours of the site's knowledge of the event using the contact details in Appendix A. All follow-up information is to be reported to the Sponsor (or an authorized representative) and documented in source as required by the Sponsor. All complaints will be monitored on an ongoing basis.

Product Complaints may require return of the product with the alleged complaint condition (syringe, pen, etc.). In instances where a return is requested, every effort should be made by the physician to return the product within 30 days. If returns cannot be accommodated within 30 days, the site will need to provide justification and an estimated date of return.

The description of the complaint is important for AbbVie in order to enable AbbVie to investigate and determine if any corrective actions are required.

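### Section 9.4 ties reporting of adverse events found on questionnaire review to relatedness and to an undefined class of authorized product, in conflict with Sections 9.0, 9.1 and 9.3

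*Combined protocol and SAP*

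**What the plan says.** The general rule in Section 9.0 is broad: "Please notify AbbVie of any adverse event whether serious or nonserious and record the information". Section 9.1 defines an adverse event as an occurrence "which does not necessarily have a causal relationship with this treatment", and says that a sign or symptom counts "whether or not the event is considered causally related to the use of the product". Section 9.3 sets the clocks, 24 hours for serious events and, for nonserious events, "from patients using an AbbVie product notify AbbVie within 15 calendar days of the physician becoming aware of the event". The collection form in Appendix F offers a causality box for events that are not related.

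Section 9.4 deals with the questionnaires in three steps. It says that their data are not regarded as a potential source of adverse events in this study. It then asks the physician to review them all the same. Finally it directs reporting to the sponsor, and to the regulator where local law requires it, under this condition: "If the physician identifies an adverse event and it is determined to be related to an AbbVie authorized product".

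On the product, Section 6.4.2 states: "The investigational products are for investigational use only". Section 11.2 uses the same qualifier for complaints: "Product complaints concerning an AbbVie authorized product must be reported to AbbVie within 24 hours".

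**The concern.** Section 9.4 is the only place in the safety section where reporting depends on a judgement of relatedness. It is also the specific rule for one source of information, and staff often follow a specific rule over a general one.

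That source matters here. Tolerability is part of the research question in the Synopsis and of the objectives in Section 5.2. The Current Symptom Survey asks about burning or stinging, blur and discomfort before the first dose and at four times up to 5 minutes after it. The Patient Eye Drop Experience Survey asks about blur after instillation at Day 14 and Day 30. Table 1 schedules biomicroscopy and staining at Screening and Baseline only, and later pressure measurement only for patients with glaucoma or ocular hypertension. After dosing starts, intolerance will therefore show mainly through what patients report.

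At stake is the completeness of the safety record. In an open-label, single-arm study, a relatedness filter makes that record depend partly on the investigator's opinion, with no comparator to set it against.

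**Working it through.** The plan states no figure on this point and no arithmetic applies. The check compares what each passage requires once the physician has identified an adverse event while reviewing a questionnaire.

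| Physician's view of the event | Sections 9.0, 9.1 and 9.3 | Section 9.4 |
|---|---|---|
| Related to ABBV-444 | Report | Report only if ABBV-444 counts as an authorized product, which is not defined |
| Not related | Report | Outside the instruction |
| Causality not determined | Report | Outside the instruction |

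1. *Rows two and three.* The conflict here does not depend on what authorized means. Sections 9.0 and 9.3 are triggered by the event and by the physician's awareness of it. Section 9.4 adds a finding of relatedness. The form's box for unrelated events shows that such events are expected to reach the sponsor.

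2. *Row one.* This depends on the undefined term. Section 6.4.2 calls the study product investigational. Section 4.1 describes an over-the-counter monograph route with no approval step before marketing, so no approval is available that would plainly make the product an authorized one. Sections 9.3 and 10.0 speak simply of an AbbVie product; the narrower phrase appears in 9.4 and 11.2.

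3. *Intent.* Section 11.0 says that product complaints are collected as part of this study. ABBV-444 is the only study product, so a reading of 11.2 that excluded it would leave that section with no study product to cover. The sponsor therefore probably meant the phrase to include ABBV-444.

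4. *Other capture.* Table 1 places an adverse event assessment at Screening, Baseline, Day 14 and Day 30/Early Exit. Every questionnaire is given at one of those visits, so an event can also be elicited directly and reported under 9.0 and 9.3.

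5. *Effect on the analysis.* Section 7 plans summaries of the OSDI, the Current Symptom Survey and the Experience Survey. It plans no adverse event rate.

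**The case against.** The strongest reply is that 9.4 says if, not only if. Nothing in it suspends 9.0 or 9.3, and a physician who notices an event on a questionnaire is aware of it, so the 9.3 clock runs. The condition may even have been meant for the added duty to inform the regulator. This is a fair reading, and it rules out the claim that 9.4 forbids reporting. It does not settle the matter. The same sentence governs reporting to the sponsor, and it follows a statement that questionnaires are not a source of adverse events, so reading it as a restriction is natural. If 9.0 already governed in full, the relatedness condition would do nothing for reports to the sponsor.

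A second reply is that the opening statement of 9.4 is deliberate: in symptomatic dry-eye patients, a poor score should not automatically become an adverse event. That stands and should be kept. The conflict concerns only events that the physician has already identified as adverse events.

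A third is that the visit-by-visit assessment gives another route. That also stands, as partial mitigation.

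A reader might infer that, because ABBV-444 is investigational, no event found on a questionnaire is ever reportable. The documents do not support this. The term is undefined, Section 11.0 points to ABBV-444 being covered, and 9.0 and 9.3 remain in force. A reader might also infer that a reported adverse event rate would be biased, but Section 7 plans no such estimate.

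**Conclusion.** The conflict is real and the passages need to be reconciled. Section 9.4 conditions reporting on relatedness, while 9.0, 9.1, 9.3 and the collection form do not; and authorized product does not clearly include the study product in 9.4 or 11.2.

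The consequence is possible under-reporting of physician-identified events. It arises only if the site takes 9.4 as the controlling rule and the event is not picked up at the scheduled assessment. The documents give no expected event rate and no indication of how the site would read the two rules, so no number of lost events can be derived. The OSDI primary endpoint and the secondary and exploratory summaries are unaffected. This is a modest correction to safety reporting, worth making because tolerability is part of the study question and the change is easy.

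**What to change.** Keep the principle at the start of 9.4, worded so that it says a questionnaire score is not in itself an adverse event. It then no longer clashes with the request that the physician review the data. Replace the conditional sentence with, for example: *If, on review of questionnaire data, the physician identifies an adverse event, it is recorded and reported to AbbVie as in Sections 9.0 and 9.3 regardless of causality, and to the regulator where local law or regulation requires it.* The last clause preserves a duty that 9.4 already contains.

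In 11.2, replace the reference to an authorized product with wording that names ABBV-444.

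The cost is a short edit to 9.4, a few words in 11.2, and possibly a few more nonserious reports. Physician identification remains the trigger, so individual scores do not become reportable by themselves.

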# 10.0 Pregnancy

If at any time you need to report a pregnancy occurrence in a patient taking an AbbVie product, the physician can notify AbbVie using the contact details in Appendix A within 24 hours of the physician becoming aware of the pregnancy.

Pregnancy is not considered an adverse event. The medical outcome for either mother or infant, meeting any serious criteria including an elective or spontaneous abortion, is considered a serious adverse event and must be reported to AbbVie using the details in Appendix A within 24 hours of the site becoming aware of the event and to the relevant Regulatory Authority, as required by local laws and regulations.

# 11.0 Product Complaint

Product complaints will be collected as part of this study; if at any time you need to report a Product Complaint (Appendix G) please refer to this section for the definition and reporting requirements.

#### 11.1 Definition

A Product Complaint is any Complaint related to the biologic or drug component of the product or to the medical device component(s).

For a product this may include, but is not limited to, damaged/broken product or packaging, product appearance whose color/markings do not match the labeling, labeling discrepancies/inadequacies in the labeling/instructions (example: printing illegible), missing components/product, device not working properly, or packaging issues.

Version date: 02 February 2023

For medical devices, a product complaint also includes all deaths of a patient using the device, any illness, injury, or adverse event in the proximity of the device, an adverse event that could be a result of using the device, any event needing medical or surgical intervention including hospitalization while using the device and use errors.

Any information available to help in the determination of causality by the device to the events outlined directly above should be reported.

#### 11.2 **Complaint Reporting**

Product complaints concerning an AbbVie authorized product must be reported to AbbVie within 24 hours of the site's knowledge of the event using the contact details in Appendix A. All follow-up information is to be reported to the Sponsor (or an authorized representative) and documented in source as required by the Sponsor. All complaints will be monitored on an ongoing basis.

Product Complaints may require return of the product with the alleged complaint condition (syringe, pen, etc.). In instances where a return is requested, every effort should be made by the physician to return the product within 30 days. If returns cannot be accommodated within 30 days, the site will need to provide justification and an estimated date of return.

The description of the complaint is important for AbbVie in order to enable AbbVie to investigate and determine if any corrective actions are required.

#### 12.0 **Privacy and Confidentiality**

#### 12.1 **Data De-Identification**

Before Personal Data is shared with AbbVie, the institution/doctor and his/her staff must replace any information that could directly identify a patient (such as name, address, and contact information) with a generic code which AbbVie cannot link to patient identity. Personal Data with identifying information may not be shared.

Version date: 02 February 2023

# 12.2 Data Storage and Access

AbbVie will store study data and any Coded Data it receives in a limited-access, secure storage space. AbbVie may retain the study data and any Coded Data reported to it for as long as AbbVie is conducting medical research in the therapeutic area that is the subject of this research or as long as the marketed product related to this research project is used, or longer, if required by EU or local laws and regulations governing research activities.

# 12.3 Reports and Publications

At the end of the study, a report or publication will be written by AbbVie. This report/publication will contain a description of the objectives of the study, the methodology and its results and conclusions. The completed questionnaires and the final study output are the confidential property of AbbVie and may not be released to unauthorized people in any form (publications or presentations) without the express written approval from AbbVie.

# 14.0 Appendices

Version date: 02 February 2023

## Appendix C. Ocular Surface Disease Index (OSDI)

## Ocular Surface Disease Index© (OSDI©)

Ask your patient the following 12 questions, and circle the number in the box that best represents each answer. Then, fill in boxes A, B, C, D, and E according to the instructions beside each.

#### HAVE YOU EXPERIENCED ANY OF THE FOLLOWING DURING THE LAST WEEK:

*	All of the time	Most of the time	Half of the time	Some of the time	None of the time
1. Eyes that are sensitive to light?	4	3	2	1	0
2. Eyes that feel gritty?	4	3	2	1	0
3. Painful or sore eyes?	4	3	2	1	0
4. Blurred vision?	4	3	2	1	0
5. Poor vision?	4	3	2	1	0

Subtotal score for answers 1 to 5

# HAVE PROBLEMS WITH YOUR EYES LIMITED YOU IN PERFORMING ANY OF THE FOLLOWING DURING THE LAST WEEK:

	All of the time	Most of the time	Half of the time	Some of the time	None of the time	
6. Reading?	4	3	2	1	0	N/A
7. Driving at night?	4	3	2	1	0	N/A
8. Working with a computer or bank machine (ATM)?	4	3	2	1	0	N/A
9. Watching TV?	4	3	2	1	0	N/A

Subtotal score for answers 6 to 9

(B)

Version date: 02 February 2023

### HAVE YOUR EYES FELT UNCOMFORTABLE IN ANY OF THE FOLLOWING SITUATIONS DURING THE LAST WEEK:

	All of the time	Most of the time	Half of the time	Some of the time	None of the time	
10. Windy conditions?	4	3	2	1	0	N/A
11. Places or areas with low humidity (very dry)?	4	3	2	1	0	N/A
12. Areas that are air conditioned?	4	3	2	1	0	N/A

Subtotal score for answers 10 to 12

ADD SUBTOTALS A, B, AND C TO OBTAIN D (D = SUM OF | SCORES FOR ALL QUESTIONS ANSWERED)TOTAL NUMBER OF QUESTIONS ANSWERED (DO NOT INCLUDE QUESTIONS ANSWERED N/A)

Please turn over the questionnaire to calculate the patient's final OSDI° score.

P24-203 - Protocol

[figure not shown]
Version date: 02 February 2023

[figure not shown]
# **Evaluating the OSDI® Score**

The OSDI® is assessed on a scale of 0 to 100, with higher scores representing greater disability. The index demonstrates sensitivity and specificity in distinguishing between normal subjects and patients with dry eye disease. The OSDI® is a valid and reliable instrument for measuring dry eye disease severity (normal, mild to moderate, and severe) and effect on vision-related function.

# **Assessing Your Patient's Dry Eye Disease**

Use your answers D and E from Side 1 to compare the sum of scores for all questions answered (D) and the number of questions answered (E) with the chart below.\* Find where your patient's score would fall. Match the corresponding shade of red to the key below to determine whether your patient's score indicates normal, mild, moderate, or severe dry eye disease.

\*Values to determine dry eye disease severity calculated using the OSDI° formula:

OSDI°= (sum of scores) x 25
(# of questions answered)

Patient's Name:	Date:	
How long has the patient experienced dry eye?		
Eye Care Professional's Comments:		
	Reference: 1. Schiffman RM, Chri Jacobsen G, Hirsch JD, Reis BL. Re of the Ocular Surface Disease Ind 2000;118:615-621. 2. Data on fil	eliability and validity ex. Arch Ophthalmol.
Toos and place in patient's chart for follow up care an part visit	PILLEDIAC	SPIRE (*)
Tear and place in patient's chart for follow-up care on next visit.	2000;118:615-621. 2. Data on fil	e, Allergan ° , Ir

P24-203 - Protocol

Version date: 02 February 2023

Strongly Disagree —	Strongly Agree
7. The study eye drops did not feel sticky. (VAS anchors: 0 = strongly disagree, 100 = strongly agree)	
Strongly Disagree ———————————————————————————————————	Strongly Agree
8. The study eye drops continued to provide relief of my eye discomfort. (VAS anchors: 0 = strongly disagree, 100 = strongly agree)	
Strongly Disagree —	Strongly Agree
9. The study eye drop continued to provide comfort to my eye dryness. (VAS anchors: 0 = strongly disagree, 100 = strongly agree)	=
Strongly Disagree —	Strongly Agree
Now think about your experience with the study eye drops over the last 24 hours after you applied them. Using the scales provided below, please mark a vertical line at the place that best describes your agreement with the following statements:	
10. The study eye drops provided relief day and night to my eye dryness (VAS anchors: 0 = strongly disagree, 100 = strongly agree)	
Strongly Disagree —	- Strongly Agree

P24-203 – Protocol
Version date: 02 February 2023

	11. The study eye drop provided comfort to my eye dryness day and night. (VAS anchors: $0 = \text{strongly disagree}$ , $100 = \text{strongly agree}$ )	
Strong	gly Disagree ———————————————————————————————————	Strongly Agree
	Lastly, think about how you have felt over the last 5 days while using the study eye drops. Using the scales provided below, please mark a vertical line at the place that best describes your agreement with the following statements:	
	12. The study eye drops provided lasting relief of my eye dryness. (VAS anchors: $0 = \text{strongly disagree}$ , $100 = \text{strongly agree}$ )	
Strong	ly Disagree ———————————————————————————————————	Strongly Agree
	13. These eye drops have provided relief during conditions that lead to eye dryness due to use of a fan, a heater, in a dry environment, digital device use, reading a book and/or watching TV (VAS anchors: 0 = strongly disagree, 100 = strongly agree, N/A)	;
Strong	aly Disagree ———————————————————————————————————	Strongly Agree

P24-203 - Protocol

Version date: 02 February 2023

